10.6. ECOG Performance Status

Data listing for ECOG performance status assessed at Screening, at each study visit, and at the EOT and EOT + 30 days visit will be provided for each patient. Patient performance status will also be summarized by treatment regimen dose group/arm and overall for each numeric grade at baseline and change from Baseline.

11. Pharmacokinetic Analyses

The plasma PK of exicorilant, enzalutamide, and major metabolites, including M2 will be characterized in the PK-Evaluable Population using noncompartmental analysis, and analyte concentration versus time plot will be provided. The following PK parameters will be calculated, whenever possible, from plasma concentrations of exicorilant, enzalutamide, and M2, and combined exposure to both enzalutamide and M2:

- AUC_{0-last} : Area under the plasma concentration-time curve calculated using linear trapezoidal summation from time 0 to time of last measurable concentration.
- AUC_{0-24} : Area under the plasma concentration-time curve from 0 to 24 hours, calculated using linear trapezoidal summation.
- AUC_{0-6h} : AUC values from time 0 to 6 hours post-dose.
- AUC_{0-inf} : Area under the plasma concentration-time curve from 0 to infinity, calculated as $AUC_{0-last} + C_{last} / \lambda_z$, where λ_z is the apparent terminal elimination rate constant (whenever possible).
- C_{max} : Maximum observed plasma concentration.
- C_{last} : Minimum concentration from time 0 to time of last measurable concentration.
- $C_{min,ss}$: Minimum observed plasma concentration, at predose at steady-state.
- CL/F : Apparent oral clearance.
- T_{max} : Time of the maximum plasma concentration (obtained without interpolation).
- T_{last} : Time after dosing of the last quantifiable concentration.
- λ_z : Terminal elimination rate constant (whenever possible).

Missing dates or times may be imputed for PK samples if the missing values can be established with an acceptable level of accuracy based on other information during the visit in question. If PK sampling for a given patient is not performed according to protocol instructions, the corresponding concentration data may be excluded from the PK analyses.

PK parameters will be tabulated and summarized by treatment at baseline and scheduled time points using descriptive statistics. PK relationship to measures of efficacy or toxicity may also be explored. Additional PK analyses may be performed as deemed appropriate.

The effect of food on the PK of exicorilant will be evaluated in the first 10 patients enrolled in Cohort A of the Expansion phase. Mean time of maximum plasma concentration (T_{\max}) will be compared in this Subcohort of patients under fed and fasting conditions, using a nonparametric test for dependent samples. The relationship of log transformed PK parameters C_{\max} , $AUC_{0-\text{last}}$, and $AUC_{0-\text{inf}}$ will be assessed with food using unadjusted and adjusted linear regression models that control for potential confounders. From these models, least-squares (LS) means, LS mean difference between fed and fasted conditions, and associated CIs will be obtained on the natural log scale. Transformed back from the logarithmic scale via exponentiation, ratios of geometric means under the two conditions and CIs will be estimated and presented. If the obtained 90% CIs for all three PK parameters fall outside the 0.80 – 1.25 range, a significant relationship between food effect and exicorilant will be concluded.

12. Pharmacodynamics and Pharmacogenomic Analyses

Biological samples (e.g., blood, plasma, serum, or tumor tissue) will be obtained from the Safety population for analysis during the study as well as for future analysis.

Summaries of actual values and changes from baseline in ACTH and serum cortisol will be presented by treatment regimen dose group, by arm and overall, for each parameter and assessment time point. Fold change in log2 scale from Baseline will be calculated as $(\log_2(\text{post-baseline measurement}) - \log_2(\text{baseline measurement})) / \log_2(\text{baseline measurement})$.

13. Change from Analyses Planned in Protocol

Definition of treatment emergent is updated from the protocol to be consistent with the definition of safety population (all patients who received at least one dose of exicorilant.) Per SAP Section 7.2 the treatment-emergent period is updated to be defined as the period of time from the date and time of the first dose of exicorilant (instead of study treatment) through 30 days after the last dose of study drug (exicorilant or enzalutamide whichever is later).

Definition of baseline is also updated from the protocol. Baseline is defined as the last measurement collected before the first dose of exicorilant (instead of exicorilant or on-study enzalutamide, whichever is earlier).

14. References

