3.1.2 Expansion Phase (Phase 2a)

Once the RD has been determined in the Dose-Determination Phase, the following cohorts will be enrolled in the Expansion Phase and treated with CORT125281 + enzalutamide according to the RD regimen. The DRC may elect to expand more than 1 dose level, if needed, to better define the RD.

- Abi-Resistant Cohort: Patients who have progressed during treatment with abiraterone and no other AR-blocking therapies (N~20)
 - Food-Effect Subcohort: The effect of food on the PK of CORT125281 will be evaluated in 10 patients enrolled to the Abi-Resistant Cohort. These 10 patients will have a 7-day Lead-In Period as follows:

- Day -7: Single oral dose of CORT125281 administered under fasting conditions
- Day 1: Single oral dose of CORT125281 administered 30 minutes after a standard breakfast. These patients will initiate enzalutamide on Cycle 1 Day 2 to avoid confounding the assessment of the effect of food on CORT125281 PK

Patients in the Abi-Resistant Cohort who do not participate in the food-effect study will not have a Lead-In Period.

- ARant-Resistant Cohort: Patients who have progressed during treatment with enzalutamide or second-generation AR-blocking therapies (N≈20). Note: Patients in the ARant-Resistant Cohort will not have a Lead-In Period.

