		6 hours ^b	
CORT125281 ^d	After a patient dose reduces and maintains dose for 2 weeks (±2 days) ^d	0 hour, pre-dose	Within 15 minutes before the dose of study treatment
		1 hour	±10 minutes
		2 hours	
		3 hours	
		4 hours	

PK, pharmacokinetic.

Note: On all days with PK assessments, CORT125281 and enzalutamide should be taken at the same time in the clinic. Both the times of the previous day's doses of CORT125281 and enzalutamide and the times of the current day's doses should be recorded.

^a. Nominal times are relative to the dose of study treatment (both CORT125281 and enzalutamide).

^b. The 6-hour PK timepoint may be omitted based upon available PK data.

^c. Must be collected after maintaining the CORT125281 dose for 14 days and prior to any dose modification.

^d. This sample only applies to those patients who require a dose reduction of CORT125281 (see Section 5.7.1) and must be collected prior to further dose modification.

Table 22 Pharmacokinetic Schedule of Assessments, Expansion Phase

PK Sample	Day	Nominal Time	Window
Both Expansion Cohorts			
CORT125281 & Enzalutamide	Cycle 2 Day 1	0 hour, pre-dose	Within 15 minutes before the morning dose of study treatment
		2 hours	±10 minutes
CORT125281 & Enzalutamide	Cycle 3 Day 1	0 hour, pre-dose	Within 15 minutes before the morning dose of study treatment
		2 hours	±10 minutes
Abi-Resistant Cohort Food-Effect Subcohort Only ^a			
CORT125281	Cycle 1 Day -7	0 hour, pre-dose	Within 15 minutes before the morning dose of study treatment
		30 minutes	Within 5 minutes of nominal time
		1 hour	
		1.5 hours	
		2 hours	±10 minutes
		3 hours	
		4 hours	
		6 hours	
		8 hours	
		12 hours ^b	±30 minutes
		24 hours	

PK Sample	Day	Nominal Time	Window
CORT125281	Cycle 1 Day 1	0 hour, pre-dose	Within 15 minutes before the morning dose of study treatment
		30 minutes	Within 5 minutes of nominal time
		1 hour	
		1.5 hours	
		2 hours	±10 minutes
		3 hours	
		4 hours	
		6 hours	
		8 hours	
		12 hours ^b	±30 minutes
		24 hours, pre-dose	

PK, pharmacokinetic.

Note: On all days with PK assessments, CORT125281 and enzalutamide should be taken at the same time in the clinic. Both the times of the previous day's doses of CORT125281 and enzalutamide and the times of the current day's doses should be recorded.

^a. Only for 10 patients enrolled in the Abi-Resistant Cohort.

^b. The 12-hour PK timepoint may be omitted based upon available PK data.

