3.1.2 Expansion Phase (Phase 2a)	
Revised text to reflect that patients in the Expansion Phase will receive CORT125281 + enzalutamide according to the RD regimen.
 
Renamed Cohorts A and B “Abi-Resistant Cohort” and “ARant-Resistant Cohort”
 
Revised the requirement for the Food-Effect Subcohort (ie, 10 patients, not necessarily the first 10 patients).
 
Added text to clarify that patients who are not in the Food-Effect Subcohort will not have a Lead-In Period.

3.2.1 Number of Patients	
Revised this text to reflect the additional patients to be enrolled for evaluation in Dose-Determination Phase Segment 2.

3.3.3 Study Duration	
Revised text to clarify that patients will receive combination treatment (CORT125281 + enzalutamide) until they reach a protocol-defined event of disease progression, experience unmanageable toxicity, or until other treatment discontinuation criteria are met.

Section	Revision
4 Study Population	Updated to reflect that patients with mCRPC with rising PSA will be allowed to enroll.

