2.4. Phase 2a, Expansion Phase

Once the RP2D has been determined in the Dose-Determination Phase, the following cohorts will be enrolled and treated with exicorilant + enzalutamide according to the RP2D regimen. The DRC may elect to expand more than 1 dose level, if needed, to better define the RP2D.

- **Abiraterone (Abi)-Resistant Cohort:** Patients who have progressed during treatment with abiraterone and have received no other AR-blocking therapies (N≈20)
 - **Food-Effect Subcohort:** The effect of food on the PK of exicorilant will be evaluated in 10 patients enrolled to the Abi-Resistant Cohort. These 10 patients will have a 7-day Lead-In Period as follows:
Day -7: Single oral dose of exicorilant administered under fasting conditions.
Day 1: Single oral dose of exicorilant administered 30 minutes after a standard breakfast. These patients will initiate enzalutamide on Cycle 1 Day 2 to avoid confounding the assessment of the effect of food on exicorilant PK.
Patients in the Abi-Resistant Cohort who do not participate in the food-effect study will not have a Lead-In Period.
- **AR Antagonist (ARant)-Resistant Cohort:** Patients who have progressed during treatment with enzalutamide or second-generation AR-blocking therapies (N≈20). Note: Patients in the ARant-Resistant Cohort will not have a Lead-In Period.

3. Study Objectives

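### SAP Section 11 defines the food-effect analysis set by a superseded enrolment-order rule that contradicts SAP Section 2.4 and the current protocol, and could exclude patients with fed and fasted profiles

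*SAP*

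**What the plan says.** The food-effect paragraph of SAP Section 11 (Pharmacokinetic Analyses) says the effect will be "evaluated in the first 10 patients enrolled in Cohort A of the Expansion phase". Its next sentence says that Tmax "will be compared in this Subcohort of patients under fed and fasting conditions".

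The other current texts set no order condition:

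- Protocol Section 3.1.2: "The effect of food on the PK of CORT125281 will be evaluated in 10 patients enrolled to the Abi-Resistant Cohort".
- Protocol Appendix A, Table 22, footnote a, on the serial fed and fasted sampling: "Only for 10 patients enrolled in the Abi-Resistant Cohort".
- SAP Section 2.4: "The effect of food on the PK of exicorilant will be evaluated in 10 patients enrolled to the Abi-Resistant Cohort".

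Protocol Section 3.1.2 also says what happens to the rest of that cohort: "Patients in the Abi-Resistant Cohort who do not participate in the food-effect study will not have a Lead-In Period". SAP Section 2.4 repeats this.

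SAP Section 1.2 says that the SAP is based on Amendment 5. SAP Section 13 lists two departures from the protocol, the treatment-emergent period and the baseline definition. The food-effect set is not among them.

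**The concern.** An order of enrolment is a selection rule, so this is more than an old cohort name. The Abi-Resistant Cohort has about 20 patients, and the current protocol lets any 10 of them form the Food-Effect Subcohort. If some subcohort patients enter 11th or later, the rule in SAP Section 11 places them outside the analysis although they have both profiles. It puts in their place earlier patients who never had a fasted dose.

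The food effect on PK is a secondary objective. Protocol Section 9.5.7 judges it by whether the 90% CIs of the fed/fasted ratios lie within 0.80 to 1.25. Fewer pairs give wider intervals. The earlier within-subject fed/fasted comparison, in Study CORT125281-600 (protocol Section 1.3.2.1), rests on 3 subjects, so each pair here carries weight. Two conflicting definitions also leave whoever programs the analysis to choose the set, possibly after the data are in hand.

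**Working it through.** **1. The texts side by side**

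| Source | Who is in the food-effect set | Order condition |
|---|---|---|
| SAP 11 | Cohort A of the Expansion Phase | Yes, first 10 |
| SAP 2.4 | 10 Abi-Resistant patients | None |
| Protocol 3.1.2 | 10 Abi-Resistant patients | None |
| Protocol Table 22, footnote a | 10 Abi-Resistant patients | None |

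The conflict is between current texts, and one side of it lies within the SAP itself. The protocol's summary of changes is used here only for intent. For Amendment 5 it records "Renamed Cohorts A and B", and it says of the food-effect patients that they are "not necessarily the first 10 patients". The wording of SAP Section 11 matches what Amendment 5 replaced.

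**2. Who can contribute a pair**

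Table 22 gives the serial profiles on Cycle 1 Day -7 (fasted) and Cycle 1 Day 1 (fed) to the Food-Effect Subcohort only. All other Expansion patients have pre-dose and 2-hour samples on Cycle 2 Day 1 and Cycle 3 Day 1. A patient outside the subcohort therefore cannot supply a fed/fasted pair, whatever his place in the enrolment order.

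**3. Pairs lost under the literal rule**

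Pairs lost = 10 - (subcohort patients among the first 10 enrolled).

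- Subcohort is the first 10 enrolled: 10 - 10 = 0 lost.
- Subcohort is the last 10 of 20: 10 - 0 = 10 lost.
- Subcohort membership unrelated to order (an assumption; the documents do not describe the order): the overlap is hypergeometric with mean 10 × 10/20 = 5 and 5th to 95th percentile 3 to 7. The chance that all 10 overlap is about 5 in a million. The cohort size is approximate: with 18 enrolled the mean overlap is 5.6, and with 22 it is 4.5.

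**4. What losing pairs would do to precision**

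The documents give no power, precision or variability basis for the 10 patients, so there is no planned figure to reproduce. The within-patient CV is assumed.

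The 90% CI for a paired comparison on the log scale is the estimated ratio multiplied and divided by exp[t(0.95, n-1) × s × √(2/n)], with s = √ln(1 + CV²).

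For CV 20%, s = √ln(1.04) = 0.198:

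- n = 10: exp(1.833 × 0.198 × 0.447) = 1.18
- n = 5: exp(2.132 × 0.198 × 0.632) = 1.31

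The other CVs follow in the same way. At a true ratio of 1:

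| Assumed CV | 10 pairs | 5 pairs |
|---|---|---|
| 20% | 0.85-1.18 | 0.77-1.31 |
| 30% | 0.79-1.27 | 0.67-1.49 |
| 50% | 0.68-1.47 | 0.53-1.89 |

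Only at CV 20% does the loss move the expected interval from inside 0.80-1.25 to outside. At 30% and above, the interval is already outside with all 10 pairs.

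**5. Whether a true ratio of 1 is plausible**

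Protocol Section 1.3.2.1 reports that in Study CORT125281-600 AUC was similar fed and fasted, while fed Cmax was about 47% lower (3 subjects). A ratio of 1 is a reasonable illustration for AUC but not for Cmax. For Cmax, take ratio 0.53 and CV 30%:

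- 10 pairs (factor 1.27): 0.53/1.27 to 0.53 × 1.27 = 0.42-0.67
- 5 pairs (factor 1.49): 0.53/1.49 to 0.53 × 1.49 = 0.36-0.79
- 3 pairs (factor 2.01): 0.53/2.01 to 0.53 × 2.01 = 0.26-1.07

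The interval stays wholly below 0.80 with 10 or 5 pairs, but not with 3.

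**The case against.** The best defence is that the phrase is only an outdated label for the Food-Effect Subcohort. The following sentence of SAP Section 11 speaks of a subcohort compared fed and fasted, with a test for dependent samples. Only Food-Effect Subcohort patients can enter such a test, so patients without profiles would drop out and add no bias. SAP Section 6.4 also requires that PK parameters can be adequately characterized. The current protocol permits the subcohort to be the first 10 enrolled, in which case nothing is lost.

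Much of this stands. Patients without profiles do no harm to a paired comparison, and the intended set can be guessed. Cohort A is simply the former name of the Abi-Resistant Cohort, so the label alone does not change the population. It is also fair that the fed conditions of Segment 2 and the Expansion Phase are already fixed on earlier PK and PD data (protocol Section 1.5.2) and do not wait for this analysis.

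The defence does not remove the order condition. The word subcohort in the second sentence points back to the 10 patients just named, so it does not restore a later-enrolled patient who has both profiles.

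A reader might go further and infer that patients with fed and fasted data are in fact dropped. The documents do not support that. They do not say which patients form the subcohort, and they report no exclusion. A loss needs both a subcohort patient enrolled after the 10th Abi-Resistant patient and a literal application of the phrase.

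**Conclusion.** Wrong as written, low severity. The inconsistency is certain: SAP Section 11 carries an order condition that SAP Section 2.4 and the current protocol do not have, and SAP Section 13 does not declare it. The consequence is conditional, with a loss anywhere from 0 to 10 of the 10 pairs depending on when subcohort patients enrol. The figure of 5 pairs rests on assumed random order, and the CI widths rest on an assumed CV and a true ratio of 1. They illustrate what could happen to AUC and do not predict a result. For Cmax, if the earlier reduction of about 47% holds, the conclusion would be the same with 10 or 5 pairs at CV 30%.

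**What to change.** In SAP Section 11, replace the enrolment-order phrase by a definition such as: all patients in the Food-Effect Subcohort of the Abi-Resistant Cohort with evaluable PK profiles on both Cycle 1 Day -7 (fasted) and Cycle 1 Day 1 (fed). If a restriction to the earliest 10 is really intended, declare and justify it in SAP Section 13 and bring SAP Section 2.4 into line.

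The cost is one SAP sentence. Sampling, dosing, sample size and the protocol stay as they are. The change should be made before the food-effect data are analysed, so that the set is not chosen with results in view.
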